# Responses (inclusive)	
5	0
10	0-1
15	Always stop with this many patients

Toxicity monitoring

In addition, toxicity will be monitored closely. Denote the probability of toxicity by T_E , where toxicity is defined as DLTs. We assume toxicity rate beta (0.66, 1.34) for the experimental treatment in this study. Our safety monitoring rule is described as follows: $\Pr(T_E > 0.33 | \text{data}) > 0.85$. That is, we will stop the enrollment in one dose if, at any time during the study, we determine that there is more than 85% chance that the DLT rate is more than 33% in that dose. Stopping boundaries corresponding to this stopping rule is listed in table 8. For example, the enrollment in one dose will be stopped if the first 4 of the first 5 patients experienced toxicity in that dose.

Table 8: Stopping boundaries for toxicity monitoring for the initial cohort of each dose (n=15)

# Patients (in complete cohorts of 5) (inclusive)	Stop the enrollment in dose level if there are this many DLTs total in that dose level:
# DLTs (inclusive)	
5	4-5
10	6-10
15	Always stop with this many patients

The operating characteristics for this design are presented in table 9. If the enrollment in one dose continues until 15 patients are evaluated in each arm and 5 CR or CRi are observed, then the 95% credible interval for the response rate would be (11.6%, 47.7%).

Table 9: Operating characteristics of the initial cohort of each dose (n=15)

True CR+CRi Rate	True DLT Rate	Early Stopping Probabilities	Average sample size treated
0.05	0.1	0.931	6.47
0.05	0.2	0.932	6.46
0.05	0.33	0.938	6.39
0.05	0.5	0.959	6.12
0.1	0.1	0.784	88.13
0.1	0.2	0.787	8.10
0.1	0.33	0.804	7.94
0.1	0.5	0.872	7.30
0.2	0.1	0.462	11.1
0.2	0.2	0.468	11.0
0.2	0.33	0.512	10.66
0.2	0.5	0.681	9.33
0.3	0.1	0.229	13.01
0.3	0.2	0.237	12.95
0.3	0.33	0.30	12.5
0.3	0.5	0.543	10.67
0.3	0.6	0.735	9.08
0.4	0.1	0.098	14.11
0.4	0.2	0.108	14.04
0.4	0.33	0.181	13.50
0.4	0.5	0.465	11.42
0.4	0.6	0.691	9.61

If three dose arms continue until 15 patients in each arm evaluated, the toxicity profile and response will be summarized for them. The dose chosen for further study will be the dose with the highest CR+CRi rate, provided that toxicity profile are also acceptable. The probability of correctly selecting the superior dose for different success rate scenarios in the three arms is summarized in table 10 below [Simon R et al 1985].

Table 10: Probability of the best arm being chosen

True Response rate in Superior Dose	True Response rate in inferior Dose 1	True Response rate in inferior Dose 2	Probability of the best arm is chosen

30%	10%	10%	86%
30%	15%	15%	71%
40%	25%	25%	63%
40%	30%	25%	56%
40%	30%	30%	50%
50%	25%	25%	83%
50%	30%	25%	78%
50%	30%	30%	73%
50%	40%	30%	59%
60%	25%	25%	94%
60%	30%	25%	91%
60%	30%	30%	89%
60%	40%	30%	79%
60%	50%	30%	63%

The arm with a favorable toxicity profile and/or a favorable might be chosen for further evaluation by expanding a cohort of 10 additional patients in that arm. We will use the same criteria (e.g. expansion will be stopped if $\Pr(T_E > 0.33 | \text{data}) > 0.85$) to monitor toxicity for the expansion cohort by using a total sample size of 25 for the winner arm. The stop boundaries are summarized in the following table. If 10 or more patients out of the 1st 20 patients experienced DLT, the trial will be stopped and no expansion cohort will be evaluated. If 10 or more patients out of 20 patients experienced DLT (by adding 5 more patients to the 15 patients in that arm), the expansion will be stopped.

Table 11. Toxicity monitoring for the expanded cohort at a dose of 75 units/m²

# Patients (in complete cohorts of 5) (inclusive)	Stop the arm with expansion cohort if there are this many dose limiting toxicities total:

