Treatment success is defined as achievement of CR or CRi. We will accrue a maximum of 15 patients at each dose level and test the null hypothesis that the true response is at most 5% (meaning little or no activity) versus the alternative hypothesis that the true response is 30% or greater, independently in each treatment arm. Assuming that the success rate is binomially distributed, this design with 15 patients in each arm has 87% power and a one-sided type I error rate of 0.05 using an exact test.

To monitor futility, the study in one dose level will be stopped early if the data in that dose level suggest that:

$$\Pr(\theta_E < 0.25 + \theta_s | \text{data}) > 0.95$$

That is, if at any time during the study we determine that there is a greater than 95% chance that the response rate is less likely to improve by 25% than the null hypothesis in one dose level, we will terminate the enrollment in that dose. Here θ_E represents the response rate for experimental drug in this study and θ_s represents the response rate for the standard practice (null hypothesis). We assume that θ_s has a distribution of beta (10, 190) to reflect the information on 200 patients for the historical data, which has a mean response rate of 0.05 and a variance of 0.0002. We also assume that θ_E has a non-informative flat prior beta(0.1, 1.9) with mean of 0.05 and variance of 0.0158.

The futility stopping boundaries for the overall response based on these assumptions and monitoring condition is shown in table 7. For example, accrual will be stopped in one dose if there is no response observed in the first 5 patients treated in that dose.

The toxicity monitoring/efficacy summary will be submitted to the IND Office Medical Monitor ([name]) for every 5 subjects treated in each Arm (per Table 7, 8, 11 & 12).

Table 7: Stopping boundaries for futility monitoring for the initial cohort of each dose (n=15)

# Patients (in complete cohorts of 5) (inclusive)	Stop the enrollment in one dose if there are this many responses total in that dose:

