	# Toxicities (inclusive)
5	4-5
10	6-10
15	8-15
20	10-20
25	Always stop with this many patients

Expansion of arm with the dose of 100 units/m²

Up to additional 25 patients will be enrolled in this arm, thus total sample size for this arm is up to 40. Assuming that the success rate is binomially distributed, 40 patients will have has 99% power to detect a difference of 5% vs. 30% in success rate at a one-sided type I error rate of 0.05 using an exact test.

Similar futility and toxicity monitoring rules listed above will also be applied for the expansion of arm with 100 units/m². That is, the trial will be stopped early if

$$\Pr(\theta_E < 0.25 + \theta_S | \text{data}) > 0.98 \text{ for futility}$$

or

$$\Pr(T_E > 0.33 | \text{data}) > 0.95 \text{ for toxicity}$$

where θ_E represents the response rate for experimental drug in this study and θ_S represents the response rate for the standard practice (null hypothesis). T_E represents DLT rate. For trial simulation, we use the same assumption for prior distributions listed above for each parameter. That is, θ_S has a prior distribution of beta (10, 190), θ_E has a non-informative flat prior beta(0.1, 1.9), and T_E has a prior distribution of beta (0.66, 1.34).

Table 12 and 13 present the corresponding stopping boundary and operating characteristics (OCs).

Table 12: Stopping boundaries for futility and toxicity of the expansion cohort with the dose of 100 units/m²

N patients evaluated	Stop for toxicity if >= this number of patients experience DLT	Stop for futility if <= this number of patients achieve CR/Ci
5	4-5	0
10	7-10	0
15	9-15	0-1
20	11-20	0-2
25	13-25	0-3
30	15-30	0-4
35	17-35	0-5
40	19-40	0-6

Table 13: OCs of the expansion cohort with the dose of 100 units/m²

True CR+CRi Rate	True DLT Rate	Early Stopping Probabilities	Average sample size treated
0.05	0.1	0.9965	8.16
0.05	0.2	0.9965	8.14
0.05	0.33	0.9969	7.99
0.05	0.5	0.999	7.26
0.1	0.1	0.9294	13.16
0.1	0.2	0.930	13.10
0.1	0.33	0.9372	12.63
0.1	0.5	0.9803	10.19
0.2	0.1	0.5119	25.54
0.2	0.2	0.5156	25.39
0.2	0.33	0.5654	24.00

0.2	0.5	0.8637	16.36
0.3	0.1	0.2029	33.50
0.3	0.2	0.209	33.30
0.3	0.33	0.2903	31.31
0.3	0.5	0.7774	20.23
0.4	0.1	0.0817	37.19
0.4	0.2	0.0887	36.96
0.4	0.33	0.1824	34.70
0.4	0.5	0.7436	22.12
0.4	0.6	0.9612	14.02

Statistical methods:

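### The 95% credible interval printed for 5 responders in 15 does not follow from the stated prior: it should be (11.4%, 53.0%), and the printed pair is what 6 in 20 would give

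*Combined protocol and SAP*

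**What the plan says.** The sentence stands in Section 10.0, between Tables 8 and 9. Its condition is "If the enrollment in one dose continues until 15 patients are evaluated in each arm and 5 CR or CRi are observed", and its conclusion is "then the 95% credible interval for the response rate would be (11.6%, 47.7"%).

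The ingredients are given elsewhere in Section 10.0:

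- **Prior.** Under Futility monitoring, the response rate for the experimental drug "has a non-informative flat prior beta(0.1, 1.9) with mean of 0.05 and variance of 0.0158". The text on expanding the 100 units/m² arm repeats it: the response rate "has a non-informative flat prior beta(0.1, 1.9), and T_E has a prior distribution of beta (0.66, 1.34"). The second distribution there is for the DLT rate. No other prior for the experimental response rate appears.
- **Model.** Responses are treated as binomial: "Assuming that the success rate is binomially distributed, this design with 15 patients in each arm has 87% power".
- **Sample size.** "We will accrue a maximum of 15 patients at each dose level" in the initial cohort.

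The sentence does not say whether the interval is equal-tailed or highest-density.

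**The concern.** A beta prior with binomial data gives a beta posterior directly, so the interval can be checked from the printed inputs, and it does not check. The printed upper limit of 47.7% looks low for an observed rate of one third in only 15 patients.

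This is the only worked interval the plan gives for the primary endpoint, and it describes the arms whose response rates decide which dose goes forward. Table 10 considers true response rates of 50% and 60%. A reader who trusts the printed interval would conclude that 5 of 15 rules out a 50% rate at the 95% level, and that a 15-patient arm pins down the response rate better than it does.

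**Working it through.** **Inputs**

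- Prior for the response rate: Beta(0.1, 1.9) (Section 10.0, Futility monitoring). Check: mean 0.1/2 = 0.05; variance 0.05 × 0.95/3 = 0.0158. Both agree with the plan.
- Data: x = 5 responders, n = 15 (Section 10.0, text before Table 9).
- Model: binomial, so the posterior is Beta(0.1 + x, 1.9 + n − x).

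**Attempt to reproduce the printed figure**

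- Posterior for 5/15: Beta(0.1 + 5, 1.9 + 10) = Beta(5.1, 11.9), mean 5.1/17 = 30.0%.
- The 2.5% and 97.5% quantiles are 0.1142 and 0.5302, so the 95% equal-tailed interval is (11.4%, 53.0%). The plan prints (11.6%, 47.7%).

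**Size of the difference**

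- Upper limit: 53.0 − 47.7 = 5.3 points too low. Lower limit: 11.6 − 11.4 = 0.2 points too high.
- Width: 47.7 − 11.6 = 36.1 points printed, against 53.0 − 11.4 = 41.6. The shortfall is 5.5/41.6, about 13%.
- Under Beta(5.1, 11.9) the printed interval holds 91.1% probability. The mass above 47.7% is 6.3%, where an equal-tailed interval leaves 2.5%.

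**Could another method explain it?** No alternative tried at 5/15 gives the printed pair:

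| Method, 5/15 | Interval |
|---|---|
| Stated prior, 95% equal-tailed | 11.4% to 53.0% |
| Stated prior, 95% highest-density | 10.1% to 51.2% |
| Stated prior, 90% equal-tailed | 13.7% to 49.1% |
| Stated prior, 90% highest-density | 12.2% to 47.2% |
| Uniform Beta(1, 1) | 15.2% to 58.7% |
| Jeffreys Beta(0.5, 0.5) | 14.0% to 58.4% |
| The plan's DLT prior, Beta(0.66, 1.34) | 13.7% to 56.6% |
| Clopper-Pearson | 11.8% to 61.6% |
| Wilson | 15.2% to 58.3% |
| Wald | 9.5% to 57.2% |

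**What data would give the printed pair?**

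- Every responder count for n = 5 to 60 was tried under the stated prior with equal tails. Only 6/20 matches: Beta(6.1, 15.9) has quantiles 0.1160 and 0.4768, that is (11.6%, 47.7%).
- Solving for the beta distribution with those two quantiles gives about Beta(6.09, 15.88). Its parameters sum to 21.97, which is 20 patients plus the prior weight of 2.

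**Side check.** The 87% power statement for 15 patients does reproduce. Declaring success at 3 or more responders has exact one-sided type I error 0.036 at a 5% rate and power 0.873 at a 30% rate.

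**The case against.** The arithmetic is not in dispute; the case on the other side concerns weight and wording.

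- **The sentence is an illustration.** The interval does not enter the futility or toxicity rules, Tables 7 to 10, or the power statement. This stands: no enrolment, stopping or selection rule depends on it.
- **The final analysis is protected.** The statistical methods paragraph of Section 10.0 plans 95% confidence intervals for each arm's CR/CRi rate from the observed data, so reported results will not inherit the wrong figure. This also stands.
- **The planning role is partly spent.** Section 4.0 already takes the 100 units/m² arm to 40 patients. True for that arm, but the sentence remains in the current text as a description of the 15-patient cohorts.
- **Only the upper limit moves materially.** Both versions exclude the 5% null rate and include 30%, and the correct posterior puts only about 4% of its mass above a 50% rate. This is fair, and it keeps the consequence small.
- **The 20-patient origin is an inference.** Correct: the documents contain no 20-patient response example, and both the sample size and the responder count must change to get the match. The error at 5/15 does not depend on where the figure came from.
- **The interval type is not stated.** The equal-tailed reading is supported by the 6/20 match, and the highest-density interval does not reproduce the printed pair either. The correction should name the type.

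**Conclusion.** The printed interval is wrong for the data it describes. Under the stated Beta(0.1, 1.9) prior and a binomial model, 5 of 15 gives a 95% equal-tailed interval of (11.4%, 53.0%). The plan understates the upper limit by 5.3 points and the width by about 13%, and so overstates the precision of a 15-patient arm, almost entirely at the upper end. The conclusion that 5 of 15 excludes a 5% rate is unaffected.

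The result rests only on the prior, the model and the counts printed in Section 10.0. Reading the interval as equal-tailed is an assumption, but no other reading tried rescues the figure. This is a definite error in the primary-endpoint text with limited consequence: worth correcting, with no bearing on how the trial is run.

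**What to change.** In Section 10.0, in the text before Table 9, replace (11.6%, 47.7%) with (11.4%, 53.0%) and state that it is the 95% equal-tailed posterior interval under Beta(0.1, 1.9). If a highest-density interval is intended, print (10.1%, 51.2%) and say so.

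The cost is one corrected line and a slightly less favourable statement of precision. The sample size, the monitoring boundaries and the operating characteristics do not depend on this figure and need no change on its account.

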- Decrease in ejection fraction: Grade ≥ 3 (nadir LVEF $<40-20\%$), related to study drug
- Creatinine elevation: Grade ≥ 3 , related to study drug.
- Any other adverse event of Grade ≥ 3 , related to study drug that in the opinion of the PI is inconsistent with the expected adverse events with standard chemotherapy.

Dose limiting hematologic toxicity is defined by bone marrow and peripheral blood examination at Day ≥ 56 showing:

- Absence of recurrent or persistent leukemia AND
- Persistently hypocellular marrow ($<20\%$ cellularity) AND
- Peripheral blood:
 - ANC < 500 and/or
 - Platelet count $< 10,000$

If more than one dose level is considered acceptably safe, the decision about which one to use for future clinical study will be based on efficacy. Efficacy success for an individual patient is defined as achievement of CR or CRI. Observation of ≤ 3 CR or CRI among 15 patients ($\leq 20\%$) defines a non-efficacious study arm. In situations where both study arms are considered equally safe, the study arm with the higher rate of response will be recommended for future study, provided it equals or exceeds 20%.

When the dose recommended for future study is defined, 10 additional newly diagnosed patients will be treated at that dose level (not to exceed a total of 25 patients at that dose level) to obtain additional evidence of safety and efficacy among previously untreated patients with high risk of induction mortality.

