10.0 Statistical Considerations(16, 17)

General Description:

This is a Phase II study of CPX-351 Liposome Injection in newly diagnosed AML patients with high risk of induction mortality. Two dose levels (50 units/m² and 75 units/m²) of CPX-351 will be studied initially. The primary objective is to evaluate treatment response. The efficacy outcome is CR or CRi within two induction cycles. A maximum of 30 patients will be equally randomized to the two dose levels. A Bayesian method by Thall et al (1995)

will be used for futility and toxicity monitoring. After 15 patients have been accrued to each dose level, an assessment of overall safety/dose limiting toxicities and efficacy will be made and one dose level will be chosen for further study. OR if both dose levels are safe and further dose escalation seems possible, one additional cohort with a dose of 100 units/m² will be open. A maximum of 15 patients will be enrolled in this arm and the same toxicity and futility monitor rules will be applied. After 2 or 3 dose levels have been studied, one dose levels will be chosen for further study. An expansion cohort of 10 patients will be treated at the dose level with a favorable response and/or toxicity profile for further evaluation for safety and efficacy. Consequently, the preferred dose level has 25 patients evaluable.

Additional 25 patients will be added to the arm with the dose of 100 units/m², the sample size for this arm will be up to 40, and the maximum number of patients for all three arms will be up to 80.

Multc Lean software version 2.1 developed in the Department of Biostatistics MDACC was used for the study design.

The study will monitor futility and toxicity, and the monitoring rules will be applied to each dose separately. If study in one of the two doses is stopped early due to futility or excessive toxicity, all the future patients will be enrolled in the open dose arm (i.e., without randomization). In the case the lower dose (50 units/m²) has been shown to be too toxic at an interim look (thus stop further patient enrollment) the higher dose (75 units/m²) will also stop accrual.

Futility monitoring:

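### Table 10: the 30/10/10 and 30/15/15 rows (86% and 71%) do not follow from the method behind the other twelve rows, and only these two change materially under the Table 7 futility stops

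*Combined protocol and SAP*

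**What the plan says.** All of this is in Section 10.0. Each dose has a cap of 15 patients in the initial stage: "We will accrue a maximum of 15 patients at each dose level". The choice among doses is by ranking, subject to acceptable toxicity: "The dose chosen for further study will be the dose with the highest CR+CRi rate". No rule for tied response counts is given. The paragraph after Table 9 opens with a condition, "If three dose arms continue until 15 patients in each arm evaluated", and then introduces Table 10: "The probability of correctly selecting the superior dose for different success rate scenarios in the three arms is summarized in table 10 below". The first two rows give 86% for true rates 30/10/10 and 71% for 30/15/15. The other twelve rows have a best arm at 40%, 50% or 60%.

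Futility is monitored during accrual, and "the monitoring rules will be applied to each dose separately". Under Table 7, "accrual will be stopped in one dose if there is no response observed in the first 5 patients treated in that dose", and also if there are 0 or 1 responses in the first 10. The Table 9 row for a 30% response rate and a 10% DLT rate reads "0.3 0.1 0.229 13.01", that is, a 22.9% chance of early stopping and a mean of 13.01 patients.

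**The concern.** Table 10 is the only operating characteristic given for the ranking step, and Section 3.1 makes selection of the most promising dose part of the primary objective. The first two rows are the ones a reader will look at first, because 30% is the alternative used in the power statement. If they came from a different calculation than the rest, the table is not comparable across rows.

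The 30% scenarios are also where the futility rule bites hardest on the best arm. A truly 30% dose that is closed early can no longer be picked, so a fixed-sample figure overstates the chance of ending with the right dose. On the printed 86%, a reader would expect the best dose to be missed in 14% of trials.

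**Working it through.** **Inputs.** n = 15 per arm and the highest-rate rule (Section 10.0); true rates and stated probabilities (Table 10); stops at 0/5 or at most 1/10 (Table 7); early-stopping probabilities (Table 9). Arms are taken as independent binomials.

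**Step 1: recover the table's method.** Let b and B be the binomial probability and cumulative probability with n = 15. The chance that the best arm wins outright, a tie counting as not correct, is

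P = Σₓ b(x; p₁) · B(x−1; p₂) · B(x−1; p₃).

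| Rates (%) | Stated | Strict winner |
|---|---|---|
| 40/25/25 | 63 | 63.4 |
| 40/30/25 | 56 | 56.1 |
| 40/30/30 | 50 | 50.2 |
| 50/25/25 | 83 | 83.0 |
| 50/30/25 | 78 | 77.7 |
| 50/30/30 | 73 | 73.2 |
| 50/40/30 | 59 | 59.0 |
| 60/25/25 | 94 | 94.1 |
| 60/30/25 | 91 | 91.4 |
| 60/30/30 | 89 | 89.0 |
| 60/40/30 | 79 | 79.47 |
| 60/50/30 | 63 | 63.0 |

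All twelve agree to the rounded percent, so the convention can be read from the table itself.

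**Step 2: apply the same formula to the first two rows.** Terms for x = 1 to 11 (later terms are negligible):

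- 30/10/10: 0.0013 + 0.0276 + 0.1132 + 0.1950 + 0.2009 + 0.1466 + 0.0811 + 0.0348 + 0.0116 + 0.0030 + 0.0006 = 0.8157, or 81.6%. Stated 86%; difference 4.4 points.
- 30/15/15: 0.0002 + 0.0093 + 0.0621 + 0.1480 + 0.1815 + 0.1423 + 0.0806 + 0.0347 + 0.0116 + 0.0030 + 0.0006 = 0.6739, or 67.4%. Stated 71%; difference 3.6 points.

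**Step 3: can a tie rule explain them?** Splitting ties at random gives 86.5% and 74.4%. The first fits 86%, but the second overshoots 71%. To reach the stated values, ties would need (86 − 81.6)/(86.5 − 81.6) = 0.90 of the split-tie credit in row 1, (71 − 67.4)/(74.4 − 67.4) = 0.51 in row 2, and none in the other twelve rows. Counting every tie as correct would only raise the figures above the split-tie values. A strict winner with n = 18 gives 85.6% and 71.6%, and rates of 25/5/5 and 25/10/10 with n = 15 give 86.7% and 71.0%. Neither uses the document's inputs, so the cause of the error is unknown.

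**Step 4: add the Table 7 stops.** The chance that an arm stops for futility is (1−p)⁵ + 5p(1−p)⁴ · (1−p)⁵. At p = 0.3 this is 0.1681 + 0.0605 = 0.2286. At rates 0.05, 0.1, 0.2, 0.3 and 0.4 it is 0.931, 0.784, 0.462, 0.229 and 0.098, which matches Table 9 at a DLT rate of 0.1. Treating a stopped arm as not selectable and enumerating again:

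| Rates (%) | Stated | Strict, fixed n | Strict, stops | Ties split, fixed n | Ties split, stops |
|---|---|---|---|---|---|
| 30/10/10 | 86 | 81.6 | 71.3 | 86.5 | 73.1 |
| 30/15/15 | 71 | 67.4 | 62.5 | 74.4 | 66.2 |

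Like for like, the stops cost 10.2 and 4.9 points under the strict rule (from unrounded values), and 13.4 and 8.2 points with ties split. For the other twelve rows the strict figure changes by at most 0.9 point.

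**Step 5: read the table conditionally.** Given that all three arms reach 15 patients, 30/10/10 is 72.8% (strict) or 80.1% (ties split), and 30/15/15 is 60.2% or 68.9%. That condition has probability 3.6% and 11.3% in the two scenarios.

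**The case against.** The best defence has four parts.

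- **The fixed-sample basis is partly disclosed.** The paragraph is conditioned on all three arms reaching 15 patients, and Table 9 just above gives the stopping probabilities. This stands as a point about disclosure. It does not rescue the two figures, because the conditional values in Step 5 are not 86% and 71% either.
- **The strict rule is inferred, not written.** This also stands. With ties split and no stops, row 1 would be right and row 2 understated. The claim that both are too high at fixed n therefore rests on the convention that the other twelve rows establish. Once the stops are included, both are too high under either tie rule.
- **The stops hardly matter elsewhere.** Correct. A reader might infer that the whole table is inflated because it leaves out futility. It is not: twelve rows change by at most 0.9 point under the strict rule, and if ties were split they would exceed the printed values even with the stops (40/30/30, for example, would be 56.9% against 50%).
- **Nothing depends on these figures.** A reader might infer that Table 10 is the plan's justification for choosing by rank. The text does not say so. The sample size rests on 5% versus 30% with 87% power, and the extra 25 patients at 100 units/m² are already committed in Sections 4.0 and 10.0. This limits the importance but does not make the two entries correct.

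**Conclusion.** The point holds in a limited form: two of 14 entries are wrong on the table's own convention, by 4.4 and 3.6 points. Against the design as it would run, with Table 7 in force and the strict rule, they are too high by 86 − 71.3 = 14.7 and 71 − 62.5 = 8.5 points. For 30/10/10, the chance of not identifying the best dose is then about 29%, not 14%.

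This assumes independent binomial arms, no selection of an arm closed for futility, and no toxicity stopping. Adding toxicity stops at a DLT rate of 0.2 lowers the figures slightly, to 70.6% and 61.9%. Section 4.0 says that 3 or fewer responses in 15 "defines a non-efficacious study arm". Requiring at least 4 responses as well as surviving futility would give 61.3% and 55.9% under the strict rule; this is a sensitivity figure only.

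The values 73.1% and 66.2% should not be taken as the right replacements. They assume random tie-breaking, which the documents nowhere state, and toxicity is also part of the dose choice.

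**What to change.** In Table 10, replace 86% with about 82% and 71% with about 67%, so that all 14 rows use one convention. Label the table as computed at a fixed 15 patients per arm, with ties counted as not correct. Add a column with the Table 7 stops applied under the same strict rule: about 71% for 30/10/10, about 62% to 63% for 30/15/15, and values within 0.9 point of the fixed-sample figures elsewhere. State in the dose-choice sentence how tied response counts are resolved; if the rule is not the strict one, recompute every row under it.

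The work is one short exact calculation. The cost is that the two 30% rows look less favourable, by about 4 points each at fixed n and by about 15 and 8 to 9 points with stops. No stopping boundary, sample size or hypothesis test changes.

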3.0 Study Objectives and Rationale

3.1 Primary Objectives

The primary objective of this study is to assess preliminary efficacy (as determined by the rate of CR or CRI) of two or three dose levels of CPX-351 in patients with newly diagnosed AML at high risk for induction mortality, defined as 30-50% predicted risk of death by Day 60, and to select the most promising dose level for further efficacy testing. Estimation of risk for induction mortality at patient screening will be based on factors associated with lower likelihood of AML response with or without factors that reduce tolerance to treatment-associated adverse events.

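### The rule for selecting a dose, which is part of the primary objective, is worded inconsistently, and Table 10 describes only one of the wordings

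*Combined protocol and SAP*

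**What the plan says.** Section 3.1 gives the primary objective two parts: to assess the CR/CRi rate by dose "and to select the most promising dose level for further efficacy testing".

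The selection rule then appears in four places.

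- **Section 4.0, Study Design.** Where more than one dose is acceptably safe, "the decision about which one to use for future clinical study will be based on efficacy". Acceptable safety is fewer than 5 DLTs in 15 patients. The same paragraph continues: "In situations where both study arms are considered equally safe, the study arm with the higher rate of response will be recommended", subject to a minimum response rate of 20%.
- **Section 10.0, General Description.** "An expansion cohort of 10 patients will be treated at the dose level with a favorable response and/or toxicity profile".
- **Section 10.0, before Table 10.** "The dose chosen for further study will be the dose with the highest CR+CRi rate, provided that toxicity profile are also acceptable". Table 10 follows, as the probability of correctly selecting the superior dose.
- **Section 10.0, before Table 11.** "The arm with a favorable toxicity profile and/or a favorable might be chosen for further evaluation", by adding 10 patients to that arm.

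Section 4.0 places the 10 extra patients at the dose recommended for future study. Choosing the arm to expand and recommending a dose are therefore one decision.

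**The concern.** Two of the wordings (Section 4.0 and the text before Table 10) make safety a gate and let response decide. The other two allow a choice on response, on toxicity, or on both, with no order or weights, and the last says only that the arm might be chosen. They part company whenever the acceptable arm with the most responses is not the one with the better toxicity profile. Two readers of the same data could then recommend different doses, and the reading could be settled after the results are known.

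Two gaps add to this. The condition of equal safety in Section 4.0 is undefined, and nothing says what happens when arms tie on response. Table 10 is the only property of the selection that the plan reports, so it matters which rule it describes.

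**Working it through.** **Inputs from the documents.** Three arms of 15 patients; the response rates in Table 10; the safety limit of fewer than 5 DLTs in 15 (Section 4.0). The documents give no DLT rates for the selection step, so every DLT rate below is an assumption.

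**Step 1: reproduce Table 10.** Let b(x; p) and B(x; p) be the Binomial(15, p) probability and cumulative probability. The chance that the superior dose has the strictly highest response count is

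P = Σ b(x; p1) · B(x−1; p2) · B(x−1; p3), summed over x = 1 to 15.

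The ties-split column adds half of each two-way and a third of each three-way tie for the top that involves the superior dose. The last column is the chance that any two or more arms share the top count.

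| True rates (%) | Table 10 | Strictly highest | Ties split | Tie for top |
|---|---|---|---|---|
| 30/10/10 | 86 | 81.6 | 86.5 | 10.9 |
| 30/15/15 | 71 | 67.4 | 74.4 | 16.1 |
| 40/25/25 | 63 | 63.4 | 70.2 | 15.9 |
| 40/30/25 | 56 | 56.1 | 63.4 | 17.3 |
| 40/30/30 | 50 | 50.2 | 57.8 | 18.7 |
| 50/25/25 | 83 | 83.0 | 87.0 | 8.7 |
| 50/30/25 | 78 | 77.7 | 82.6 | 10.6 |
| 50/30/30 | 73 | 73.2 | 78.7 | 12.3 |
| 50/40/30 | 59 | 59.0 | 65.8 | 15.6 |
| 60/25/25 | 94 | 94.1 | 95.8 | 3.5 |
| 60/30/25 | 91 | 91.4 | 93.7 | 4.8 |
| 60/30/30 | 89 | 89.0 | 91.8 | 6.0 |
| 60/40/30 | 79 | 79.5 | 84.0 | 9.6 |
| 60/50/30 | 63 | 63.0 | 69.5 | 13.6 |

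Twelve of 14 rows match the strict rule within 2 points. The first two rows do not, and no single variant tried at n = 15 gives both. Table 10 therefore uses response only, with no DLT term and no early stopping, and counts ties as failures.

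**Step 2: add the plan's own safety gate.** An arm with true DLT rate d passes with probability B(4; d): 98.7% at 10%, 83.6% at 20%, 51.5% at 30%. Take the strictly highest response among passing arms, with response and DLT treated as independent. DLT rates are listed with the superior-response dose first.

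| Response rates | Table 10 | DLT 10/10/10 | DLT 20/20/20 | DLT 30/20/10 |
|---|---|---|---|---|
| 50/30/30 | 73 | 72.5 | 64.0 | 38.6 |
| 60/30/30 | 89 | 88.0 | 75.7 | 46.3 |

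Even the highest-response rule departs from Table 10 once the gate is applied.

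**Step 3: let toxicity decide.** The extreme reading of the and/or wording is to choose the arm with fewest DLTs, ties split. The chance that this is the superior-response dose does not depend on the response rates:

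- DLT 10/20/30%: 73.7%
- DLT 20/20/20%: 33.3%
- DLT 25/20/15%: 16.2% (10.3% if ties count as failures)
- DLT 30/20/10%: 5.5%

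A middle reading, responses minus DLTs with ties split, gives about 70% (DLT 20/20/20%) and 42% (DLT 30/20/10%) for the 50/30/30 row. Response alone with ties split gives 78.7%.

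**The case against.** The strongest reply is that a specific rule exists and is stated twice, in Section 4.0 and directly before Table 10. The and/or wording sits in a general description and in a sentence that has lost a word. It is looser, and includes the specific rule as one reading. That is fair, and it makes this an inconsistency to reconcile more than two rival designs. It does not remove the point: the General Description carries the full phrase, so nothing turns on the missing word.

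Three stronger inferences are tempting and are not supported.

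- **That Table 10 is void.** It follows the rule it describes and largely reproduces under it. It simply does not cover a choice in which toxicity plays a part.
- **That equally safe means equal DLT counts**, so that arms with 1/15 and 4/15 fall under different rules. The paragraph opens with doses considered acceptably safe, and the phrase can be read as both arms passing the limit of fewer than 5 in 15. Both arms then pass and response decides. The fault is that the term is undefined.
- **That 10% or 16% is the expected chance of choosing the best-responding dose.** No passage says the arm with fewest DLTs is chosen. That figure is one adverse point on assumed rates, and all three arms pass the gate together in only 0.686 × 0.836 × 0.938 = 54% of such trials. Given that all pass, the figures are 12% and 20%.

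The practical reach is also limited. The current text already takes 100 units/m² to 40 patients, and the title of Table 11 already names 75 units/m².

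**Conclusion.** The point holds as an inconsistency in a decision rule that belongs to the primary objective. The four statements do not give one rule, equal safety is undefined, and there is no tie rule although ties for the top response occur in 3.5% to 18.7% of trials in the table's own scenarios. Table 10's 50% to 94% applies to a strictly highest response with toxicity, the DLT gate and early stopping left out; it is unsupported if toxicity enters the choice. The range of about 5% to 74% shows how far an extreme reading could move the result. It rests wholly on assumed DLT rates and is not a forecast.

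The plan should be corrected, but the weight is moderate: the final recommendation is mainly what remains open.

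**What to change.** Reconcile Section 4.0 and the three statements in Section 10.0 to one prespecified selection rule. There are two ways to do so, and the choice between them is the investigators'.

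1. Align the other passages to the rule before Table 10, which is the one the table assumes. Replace the condition of equal safety with meeting the Section 4.0 safety criterion, remove the and/or and might wording, and add a tie rule.
2. If toxicity is meant to influence the choice among acceptable doses, state in advance how it does so, including ties, and recompute Table 10 for that rule over a stated range of DLT rates.

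In either case, note beside Table 10 that it ignores the DLT gate and early stopping and counts ties as failures, and check its first two rows. Section 4.0 should also settle the minimum response: it calls 3 of 15 (20%) non-efficacious and, two sentences later, sufficient for a recommendation.

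The cost is wording in four places and, for the second option, one short calculation. No new data are needed. The price is less discretion once the data have been seen.
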